**6.2.1. General Monitoring Principles**

### 6.2.1. General Monitoring Principles

The following cardiac monitoring guidelines are required for this study:

1. Patients in screening will have a baseline ECG performed to determine eligibility.
2. Enrolled patients will have ECGs collected as defined in Table 1.
3. On treatment days when ECGs are to be obtained, the patient will take their medication in the clinic. Prior to the first dose of panobinostat (Cycle 1, Day 1), the QTcF interval from each of the 3 ECGs must be  $\leq 450$  msec and the average of the pretreatment QTc intervals must be  $\leq 450$  msec before the patient is dosed. This real-time assessment will be based on the QTc intervals as determined at the clinical center.
4. If the patient does not meet the QTc criteria for dosing, the patient's serum potassium, magnesium, calcium and phosphorus must be measured immediately, and the patient must receive supplements to correct any low values.
5. If the patient experiences a QTcF  $> 480$  msec in Cycle 1 or in any subsequent cycle, the Cycle 1 ECG monitoring schedule will be repeated until they have a treatment cycle with no QT prolongation.
6. At any time, if any ECGs (baseline or post-dose) demonstrate a QTc value  $\geq 480$  msec the Investigator must notify the Sponsor immediately. In addition, the patient's serum potassium, magnesium, calcium and phosphorus must be measured immediately, and the patient must receive supplements to correct any low values.
7. All ECGs will be reviewed by the treating physician prior to administering the dose of panobinostat.
8. In general, panobinostat dose reductions or discontinuations will occur in the following circumstances:
  - Repeat dosing delays due to prolonged QTc intervals
  - QTc  $\geq 480$  msec but  $< 500$  msec (in absence of electrolyte abnormalities).
  - Any QTc  $\geq 500$  msec (discontinuation).

For patients requiring a dose reduction, 3 pre-dose ECG's will be done on the first day of the new lower dose, and 3-hours post-dose (x 3).

If however, it was determined that the QTc prolongation was secondary to electrolyte abnormalities or concomitant medications, panobinostat may be continue at the same dose level. ECGs will be repeated - pre-dose (x3), 3-hours post-dose (x3), on the next scheduled dosing day.

9. Any QTc  $\geq 500$  msec will lead to discontinuation of the panobinostat.
10. All other cardiac events should be treated as per the local standard of care and referred to a specialist by the investigator (if clinically indicated).

11. If no significant QTcF prolongation is noted during the first 8 cycles, the QT monitoring is no longer required and may be performed at the Investigator's discretion.

**Any patient who has an ECG with a QTc  $\geq$  500 msec must be monitored very closely.** Check and correct the patient's serum potassium, magnesium, calcium, and phosphorus immediately.

If any QTc interval is  $\geq$ 500 msec, the patient must have at a minimum, hourly ECG monitoring until the QTc is  $<$ 480 msec. In addition to the minimum hourly ECG monitoring, telemetry monitoring is strongly recommended. Prior to a patient with a QTc interval  $>$ 500 msec being discharged to home, that patient must have at least 2 consecutive, hourly ECGs obtained at least 6 hours after dosing that demonstrate a QTc interval of  $\leq$ 480 msec.

If any patient has a QTc interval  $\geq$ 500 msec, the Investigator must notify the Sponsor immediately. The patient must not receive any further doses of panobinostat and must be discontinued from the study.

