## **6. DOSE MODIFICATIONS**

The criteria for interruption and resumption of treatment due to toxicity are outlined in the following tables. Dose re-escalation will not be allowed in any patient. All toxicities will be graded utilizing the NCI CTCAE v4.0. If toxicity occurs, the toxicity will be graded, and appropriate supportive care treatment will be administered to decrease the signs and symptoms thereof. If one drug is held, treatment may continue with the other study drug as appropriate. If study medication is held for over 3 weeks due to toxicity, that study medication will be discontinued. Treatment medications will be adjusted with a one level dose-reduction. The dose level criteria in Table 3 should be used to adjust the panobinostat or carfilzomib dose in the event of toxicity. If patients who are on the lowest allowable dose have a toxicity requiring dose reduction, the offending agent should be discontinued. Either or both drugs may be adjusted according to the dose modification tables below.

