**6.2. Panobinostat Dose Modifications for Prolonged QTc Interval**

All cardiac events should be treated according to institutional standards and referred to a specialist if clinically indicated. Treatment decisions at the sites will be based on QTc as determined by the automated machine reading (or as measured and calculated by trained personnel at the site). If a patient cannot be dosed due to prolonged QTcF for more than 7 days since last dose, patient should be discontinued from study.

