**Table 7: Criteria for Dose Reductions, Delays and/or Re-Institution Due to Drug-Related QTcF Abnormalities**

ECG TIME POINT	ABNORMALITY	DOSE MODIFICATION GUIDELINE
Dose modifications are based on local readings of the average QTcF of triplicate ECGs.		
Cycle 1 Dose Modification Criteria:		
Cycle 1 PRE-DOSE Days 1 and 5 Triplicate ECGs	Day 1: Average QTcF: >450 msec	Check and correct the patient's serum potassium, magnesium, calcium, phosphorus immediately, as well as evaluate concomitant medications. If abnormality noted on Cycle 1 Day 1: Repeat 3 pre-dose ECGs. If the 3 pre-ECGs: Do not meet criteria again, discontinue patient from study. Do meet criteria for dosing; administer panobinostat.
	Day 5: Average QTcF: ≥480 msec to <500 msec Or >60 msec increase from baseline average	If abnormality noted on Cycle 1 Day 5: Delay dose at least 3 days and repeat 3 pre-dose ECGs. If the repeat 3 pre-dose ECGs: Do not meet pre-dose ECG criteria again, discontinue panobinostat. Do meet pre-dose ECG criteria for dosing and QTc prolongation determined to be related to panobinostat, resume panobinostat treatment with a 1-level dose reduction. If however, it was determined that the QTc prolongation was secondary to electrolyte abnormalities or concomitant medications, continue at the same dose level. Repeat ECGs – pre-dose (x3), 3-hours post-dose (x3), on the next scheduled dosing day.
	Average QTcF: ≥500 msec	Check and correct the patient's serum potassium, magnesium, calcium and phosphorus immediately. Discontinue patient from panobinostat.  If however, it was determined that the QTc prolongation was secondary to electrolyte abnormalities or concomitant medications: Omit dose. On the next scheduled dosing day continue at the same dose level. Repeat ECGs - pre-dose (x3), 3-hours post-dose (x3), on the next scheduled dosing day.

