**Table 7. Criteria for Dose Reductions, Delays, Re-Institution Due to Drug Related QTcF Abnormalities (continuation)**

ECG TIME POINT	ABNORMALITY	DOSE MODIFICATION GUIDELINE
Dose modifications are based on local readings of the average QTcF of triplicate ECGs.		
Cycle 1 Dose Modification Criteria:		
Cycle 1 POST-DOSE Days 1 and 5 Triplicate ECGs	Average QTcF: ≥480 msec to <500 msec Or >60 msec increase from baseline average	Check and correct the patient's serum potassium, magnesium, calcium, phosphorus immediately, as well as evaluate concomitant medications. Monitor ECG hourly or by telemetry until at least 2 consecutive hourly ECGs performed at least 6 hours post dose are <480. Next scheduled dosing day: repeat 3 pre-dose ECGs. If these 3 pre-dose ECGs: Do not meet pre-dose ECG criteria for dosing (average QTcF ≥480 msec), discontinue patient from study. Do meet pre-dose ECG criteria for dosing (average QTcF <480 msec) and QTc prolongation determined to be related to panobinostat, resume panobinostat treatment with a 1-level dose reduction. If however, it was determined that the QTc prolongation was secondary to electrolyte abnormalities or concomitant medications, continue at the same dose level. Repeat ECGs - pre-dose (x3), 3-hours post-dose (x3) on the next scheduled dosing day.
	Average QTcF: ≥ 500 msec	Check and correct the patient's serum potassium, magnesium, calcium and phosphorus immediately. Discontinue patient from panobinostat. If however, it was determined that the QTc prolongation was secondary to electrolyte abnormalities or concomitant medications: omit dose. On the next scheduled dosing day continue at the same dose level. Repeat ECGs - pre-dose (x3), 3-hours post-dose (x3), on the next scheduled dosing day.

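### Cycle 1 average QTcF of 500 msec or more from a correctable cause: Table 7 re-doses panobinostat, Section 6.2.1 forbids it, and the protocol does not settle which rule prevails

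*Combined protocol and SAP*

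**What the plan says.** Four texts govern a QTc of 500 msec or more.

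- **Table 7 (Cycle 1).** Both rows for an average QTcF of 500 msec or more, pre-dose and post-dose, stop panobinostat by default. Both then make an exception for electrolyte or concomitant-drug causes. The pre-dose row omits the dose and adds: "On the next scheduled dosing day continue at the same dose level". The post-dose row reads: "secondary to electrolyte abnormalities or concomitant medications: omit dose. On the next scheduled dosing day continue at the same dose level". Triplicate ECGs are repeated on that day. The trigger is in the table header: "Dose modifications are based on local readings of the average QTcF of triplicate ECGs".
- **Section 6.2.1, item 8.** Under a general introduction it lists three circumstances for reducing or stopping panobinostat, one of them any QTc of 500 msec or more (discontinuation). It then says that, for the same two kinds of cause, "panobinostat may be continue at the same dose level". It gives no upper QTc limit.
- **Section 6.2.1, item 9.** Any QTc of 500 msec or more "will lead to discontinuation of the panobinostat". No cause is excepted.
- **Section 6.2.1, closing paragraph.** After notification of the Sponsor: "The patient must not receive any further doses of panobinostat and must be discontinued from the study". Again no cause is excepted.

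Two general rules also bear on the case. Section 6 says: "If one drug is held, treatment may continue with the other study drug as appropriate". Section 6.2 says: "If a patient cannot be dosed due to prolonged QTcF for more than 7 days since last dose, patient should be discontinued from study".

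**The concern.** Two sites with the same Cycle 1 tracing and the same explanation for it could each follow the protocol and act in opposite ways. One omits a dose and gives the same dose of a QT-prolonging drug again. The other stops the drug for good, or takes the patient off study and so ends carfilzomib as well. The case is one the protocol itself foresees: Section 8.1.5 lists diarrhea among the most frequent panobinostat effects and changes in blood electrolytes among the others. What is at stake is the safety of individual patients and consistent conduct across sites.

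**Working it through.** The plan gives no figure to reproduce here, so the main check is a comparison of texts.

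**1. Do both rules reach the same patient?** The largest of three readings is at least their mean. An average QTcF of 500 msec or more therefore includes at least one reading of 500 msec or more. Every patient in a Table 7 row for 500 msec or more also meets the trigger in Section 6.2.1.

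**2. What does each text require?**

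| | Table 7, rows for 500 msec or more | 6.2.1 item 9 | 6.2.1 closing paragraph |
|---|---|---|---|
| Trigger | Average of triplicate ECGs, Cycle 1 | Any QTc | Any QTc |
| Electrolyte or concomitant-drug cause | Omit a dose, then same dose level | Stop panobinostat | Stop panobinostat, off study |
| Other cause | Stop panobinostat | Stop panobinostat | Stop panobinostat, off study |

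The middle row is the main conflict. The last row shows a second one that does not depend on cause: Table 7 and item 9 end panobinostat only, while the closing paragraph ends participation.

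**3. Does the trigger differ?** Take readings of 505, 485 and 480 msec. The average is (505 + 485 + 480) / 3 = 1470 / 3 = 490 msec. Table 7 uses its 480 to under 500 msec row, which allows treatment to resume. Section 6.2.1 sees one reading of 505 msec and stops the drug.

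**4. How often could it happen?** Inputs are from Sections 1.2.2 and 1.2.3. The two schedule rates count values above 500 msec, so they slightly undercount values of 500 msec or more.

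- Three times weekly, every other week: 0 of 70. Exact two-sided 95% upper limit = 1 − 0.025^(1/70) = 5.1%. For 80 patients: 80 × 0.0513 = 4.1. This is a confidence bound on zero observed events, not an expectation.
- Three times weekly, every week: 3 patients, printed as 0.5%, two of them at 20 mg. If that rate applied here: 80 × 0.005 = 0.4 patients expected, and the chance of at least one is 1 − 0.995^80 = 33%.
- Panobinostat with bortezomib: none of 2,200 ECGs showed a QTcF above 480 msec.

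These figures cover all cycles and all causes. The documents do not give the share that falls in Cycle 1 with an electrolyte or concomitant-drug cause, so the count relevant to the main conflict is smaller by an unknown factor.

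**5. Does the seven-day rule interact?** Cycle 1 panobinostat days are 1, 3, 5, 15, 17 and 19. If Day 5 is omitted for QTcF, Day 15 is 15 − 3 = 12 days after the last dose. If Day 15 is omitted, Day 17 is 17 − 5 = 12 days after the last dose. Both exceed 7 days. The Day 5 to Day 15 interval alone is 10 days and is planned for every patient, so by itself it is not a delay caused by QTcF. After a Day 1 post-dose event, dosing on Day 3 or Day 5 falls within 7 days.

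**The case against.** The strongest reply is that the protocol does indicate which text governs. The ECG monitoring text in Section 5.1.1.1 sends the reader to Section 6.2.1 for monitoring and to a table (misnumbered as Table 6) for management of prolonged QTc. Item 8 points the same way. Its exception follows all three listed circumstances, including 500 msec or more, and the 480 to under 500 msec bullet already carries its own electrolyte qualifier, so an exception confined to that range would be partly redundant. The same-dose exception appears three times, which suggests intent.

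This stands as evidence of a lean towards Table 7. It does not settle precedence. Section 6.2.1 introduces its guidelines as required, item 9 and the closing paragraph come after item 8, and both are unconditional. If item 8 does cover 500 msec or more, Section 6.2.1 contradicts itself.

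It is also fair to say that safeguards exist: electrolytes must be at or above the lower limit of normal before re-dosing, triplicate ECGs are repeated, and the Sponsor is told at once. These lower the risk. They do not tell the Sponsor or the site which rule to apply.

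A reader might infer more than the documents support:

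- **DLT scoring.** Section 5.2.2 counts only events related to study treatment, and its missed-dose criterion concerns both agents, missed because of toxicity. The event here is attributed to electrolytes or other drugs, and item 9 does not itself stop carfilzomib.
- **Exact Cycle 1 dose fractions.** The post-dose row of Table 7 does not say which dose is omitted, and Section 6.3 holds both drugs for grade 3 or higher events, so no single fraction is firm.
- **The seven-day rule makes Table 7 unusable after any Day 5 event.** That would count the planned gap as a QTcF delay. A question remains only when the Day 5 or Day 15 dose is itself omitted for QTcF.

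**Conclusion.** The point holds in this form. For a Cycle 1 average QTcF of 500 msec or more attributed to electrolytes or concomitant drugs, Table 7 continues panobinostat at the same level after an omitted dose. Item 9 and the closing paragraph of Section 6.2.1 forbid further panobinostat. Both instructions cannot be followed, and the text that leans towards Table 7 does not resolve the matter. The texts also disagree on whether the patient leaves the study and on whether one reading or the average counts.

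The event is rare: 0 of 70 with an upper limit of 5.1%, or about 0.4 of 80 patients if the 0.5% weekly-schedule rate carried over. Both figures precede the restriction to Cycle 1 and to these causes, and both assume that earlier panobinostat experience applies to this combination. No effect on DLT scoring or on the response endpoint is claimed. The reason to act is that contradictory stopping rules for a QT-prolonging drug are a patient-safety matter that a text change can remove.

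**What to change.** State one rule, in the same words, in Table 7, in items 8 and 9, and in the closing paragraph of Section 6.2.1. The clinical team chooses between:

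- **(a) No exception.** Delete the same-dose exception from both Table 7 rows for 500 msec or more, and limit the item 8 exception to 480–499 msec.
- **(b) Keep the exception.** Write it into item 9 and the closing paragraph. Say which dose is omitted after a post-dose ECG. Say how the seven-day rule in Section 6.2 applies when the Day 5 or Day 15 dose is omitted for QTcF.

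Until that choice is made, sites follow the stricter rule. Under either option, state whether 500 msec or more ends panobinostat only or study participation, and whether the trigger is the triplicate average or any single reading.

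The cost is wording in one amendment and a site memo, with no new procedures. Under (a), a rare patient with a correctable cause loses panobinostat, and carfilzomib too if participation ends. A single-reading trigger is more cautious but lets one reading end treatment when the average is below 500 msec.

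Editorial note only, not part of the case above: in the AST/ALT block of Table 6, replace the bilirubin line with AST/ALT above 10 x ULN. Correct the table references: 3 to 4 in Section 6, Tables 5 and 6, and Section 6.3; 6 to 7 in Section 5.1.1.1; 7 to 8 in Section 6.3; 4 to 5 in the infection row of Table 8.

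### Cycle 1 QTcF averaging 500 msec or more with a correctable cause: Table 7 resumes panobinostat at the same dose, while Section 6.2.1 bars it and takes the patient off study

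*Combined protocol and SAP*

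**What the plan says.** Four places in Section 6.2 govern a QTc of 500 msec or more.

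- **Table 7, Cycle 1 pre-dose row.** For an average QTcF of 500 msec or more, electrolytes are checked and corrected and panobinostat is discontinued. If electrolytes or concomitant medication explain the value, the dose is omitted instead, and then: "On the next scheduled dosing day continue at the same dose level".
- **Table 7, Cycle 1 post-dose row.** The same, with the same exception: "omit dose. On the next scheduled dosing day continue at the same dose level".
- **Section 6.2.1, items 8 and 9.** Item 8 lists general circumstances for reducing or stopping panobinostat, and its third bullet marks 500 msec or more as a discontinuation. A paragraph after the list adds an exception for prolongation that was "secondary to electrolyte abnormalities or concomitant medications, panobinostat may be continue at the same dose level". It states no QTc limit. Item 9 then says that any QTc at or above 500 "msec will lead to discontinuation of the panobinostat", with no exception.
- **Section 6.2.1, closing paragraph.** For any patient with a QTc of 500 msec or more, the sponsor must be notified at once, and "The patient must not receive any further doses of panobinostat and must be discontinued from the study". It gives no exception.

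Table 7 states that its criteria apply to the average of triplicate ECGs read locally. Item 9 and the closing paragraph apply to any QTc.

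**The concern.** An investigator who sees a Cycle 1 average of 500 msec or more in a patient with low potassium can find two opposite orders within one section. Under Table 7 the patient skips a dose and takes the same panobinostat dose on the next dosing day. Under the end of 6.2.1 the patient never takes panobinostat again and leaves the study, which ends carfilzomib as well.

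This is the level at which the protocol itself requires hourly ECGs and strongly recommends telemetry. Different sites could therefore handle the same event in opposite ways. What is at stake is patient safety and consistency of the treatment received. Section 5.1.1.1 makes it more likely that a site goes to the table first, because it sends readers to a table for managing prolonged QTc. It cites Table 6, which now covers other non-hematologic toxicities; the QTc table is Table 7.

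**Working it through.** The plan gives no figure to reproduce here. The main check sets the texts side by side.

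**1. Cycle 1, average QTcF of 500 msec or more, correctable cause**

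| Text | Panobinostat | Patient |
|---|---|---|
| Table 7, pre-dose and post-dose rows | omit one dose, then same dose | stays on treatment |
| 6.2.1 item 8 exception | may continue at same dose, if it reaches this band | not stated |
| 6.2.1 item 9 | stopped | not stated |
| 6.2.1 closing paragraph | no further doses | off study |

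Rows 1 and 4 cannot both be obeyed, nor can rows 1 and 3.

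**2. Does average versus any reading reconcile them?** No. If all three readings were below 500 msec, their mean would be below 500 msec. A mean of 500 or more therefore needs at least one reading of 500 or more. Every patient in a Table 7 row for 500 msec or more also meets the 6.2.1 trigger.

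**3. Does the trigger differ in the other direction?** Yes. Illustrative readings of 505, 480 and 470 msec give (505 + 480 + 470)/3 = 1455/3 = 485 msec. Table 7 places this in its row for 480 to below 500 msec, where panobinostat can resume if the repeat ECGs pass. The 505 reading alone takes the patient off study under the closing paragraph of 6.2.1.

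**4. Same band, no correctable cause.** Table 7 and item 9 stop panobinostat. The closing paragraph stops panobinostat and takes the patient off study. A site that does the latter has obeyed all three, so this is a difference of scope and not a contradiction.

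**5. How often?** Inputs are the background rates in Sections 1.2.2 and 1.2.3 and the maximum of 80 patients.

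- Three times weekly: 3 patients above 500 msec, stated as 0.5%. 80 × 0.005 = 0.4 patients.
- Three times weekly every other week, the schedule closest to this trial: 0 of 70. 80 × 0/70 = 0 patients. The one-sided 95% upper bound is 1 − 0.05^(1/70) = 0.0419, and 80 × 0.0419 = 3.4 patients.
- Panobinostat with bortezomib in myeloma: 2,200 ECGs, none above 480 msec and no rise above 60 msec from baseline.

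The Section 1.2.2 rates are not limited to Cycle 1, whereas Table 7 covers only Cycle 1. They also include events without a correctable cause, a share the documents do not give. Both points make the number meeting the direct conflict smaller than these figures.

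**The case against.** The best defense is that the stricter text plainly governs. Section 6.2.1 opens with "The following cardiac monitoring guidelines are required for this study" and ends in mandatory terms, while Table 7's action column is labelled a guideline. Item 9 follows the item 8 exception and can be read as its upper limit. The sponsor also hears of the event: for a QTc at or above 480 "msec the Investigator must notify the Sponsor immediately", and the closing paragraph repeats this at 500 msec. There is time to settle the matter before the next dose.

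Much of this stands. The item 8 exception is ambiguous, and it should not be counted as a clear permission to re-dose at 500 msec or more. Mandatory wording does favor stopping. But Table 7's exception is written inside the rows for 500 msec or more, so no reading of item 8 removes it, and no sentence ranks the table below 6.2.1. Notification is a duty to report. Nothing makes re-dosing wait for the sponsor's answer, and Section 6.2 says: "Treatment decisions at the sites will be based on QTc as determined by the automated machine reading". That sentence concerns which reading is used and does not exclude sponsor direction, but it does leave the decision at the site.

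It is also fair to object that Table 7 has no criteria after Cycle 1. From Cycle 2, when a single pre-dose ECG is normally scheduled, 6.2.1 stands alone and there is no clash.

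**Conclusion.** The contradiction is real and narrow. It covers Cycle 1 patients with an average QTcF of 500 msec or more attributed to electrolytes or concomitant medication. The mismatch between the triplicate average and any single reading, also in Cycle 1, is a second genuine inconsistency.

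Three stronger readings are tempting, and the documents do not support them.

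- A reader might infer that every patient at 500 msec or more faces incompatible orders. Without a correctable cause, all the texts can be obeyed by leaving the study. The scope should be aligned, but nothing contradicts.
- A reader might infer that item 8 expressly permits re-dosing at 500 msec or more. It states no limit, but item 9 may supply one.
- A reader might infer damage to the efficacy analysis. The response endpoint is not redefined, and Section 7.6.1 continues follow-up for progression and survival in patients who stop treatment early.

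The expected size is well under one patient in 80, assuming the background rates carry over to this combination. The 0 of 70 is a small sample and does not exclude a few patients. The point should be corrected because it is a cardiac-safety dosing rule with two answers, not because many patients will meet it.

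**What to change.** Adopt the stricter rule that the closing paragraph of 6.2.1 already contains.

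1. In both Table 7 rows for 500 msec or more, delete the exception for electrolytes and concomitant medication. End each row with: *no further panobinostat; discontinue patient from study*.
2. Limit the exception under item 8 to QTc below 500 msec, and say that it includes rises of more than 60 msec from baseline, for which Table 7 keeps the exception.
3. Add discontinuation from the study to item 9.
4. State in Table 7 that any single QTc of 500 msec or more triggers this rule and overrides the milder row. Keep the triplicate average for the milder band.

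The cost is one wording amendment to two Table 7 rows, a trigger note, and items 8 and 9, with the IRB submission that Section 13.1 requires. No ECGs or visits are added. The clinical downside is that a rare patient with a correctable cause loses both drugs. If the sponsor's clinicians prefer to keep the exception, it should instead be written into item 9 and the closing paragraph, with a statement on whether carfilzomib continues.
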